We plan to recruit a total of **440 patients**, including 220 African Americans and 220 White patients. We will recruit patients in the order they are identified as eligible and interested, but we will attempt to recruit no more than **60 total** patients per physician, half who self-identify as Black/African American and half who self-identify as White. Further, we will recruit family members and other health care providers that may appear in our video recordings. We anticipate recruiting a total of **200 family members** and **100 other health care providers**. Considering the fact that many patients may never become eligible for an available trial or may leave the study for medical or social reasons, we estimate that approximately 216 of these participants will be eligible for a clinical trial. Thus, **our estimated sample for the primary analyses is 216 patients who will be video recorded discussing a trial with a participating physician**. We will recruit half of the patient sample (i.e., 220 AA and White men) as quickly as possible following their physician's consent at the beginning of data collection (the first 20 months/pre-physician intervention). These patients will actively participate until they either receive a trial offer or until the physician intervention is implemented. We will recruit the second half of the patient sample

(also 22) AA and White men) immediately following the physician intervention; these patients will participate actively until they receive a trial offer or until data collection ends.

[figure not shown]
Study Design, Interventions, and Measures

Study Design Overview (See Figure 2). This 5-year study involves two related interventions and research designs conducted over a 42-month data collection period. These interventions begin after IRB approval is received and physicians are consented.

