Power and Sample Size Estimates. A within-subject design is used to evaluate the physician intervention and a randomized control trial is used to evaluate the patient intervention. However, the outcomes of both interventions will be modeled at the patient level in a single model. We used the person-level multi-site/block trial design within Optimal Design to conduct power analyses because the unit of analysis is the patient-physician visit and data from these visits will likely be more similar within physicians than between physicians. The first power analysis is based 216 patients not lost to attrition, who should be eligible for clinical trials and thus randomized into the patient-level intervention. (See Participants and Recruitment—p. 7) We define the *primary outcome* of our study as patients' decisions to enroll in clinical trials, where a "success" is defined as a patient deciding to enroll. Our primary objective (Aim 1) is to examine the extent to which patient- and physician-level interventions affect physician and patient trial-related decisions, and thus we seek a sample size that gives us sufficient power to detect both the main effect of intervention and important interaction effects. We chose GEE power analysis for nested binomial outcomes with within-cluster treatments⁶⁶ as the best available model to estimate power for our primary objective; such estimates are lacking for HLM models. With 24 physicians and 9 patients per physician (i.e., 216 patients), a Type I error rate (α) of .05, and ICC of .05, and probability of success under the null hypotheses (p_{H_0}) of .25, we are well powered to detect p_H of .35 ($b = 0.48$, odds-ratio = 1.61) with power > .99. Our secondary objective, (i.e., Aim 2) is to examine whether patient race influences the effectiveness of either patient- or physician-level interventions on our primary outcome, and we remain well

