Control variables: At the patient level of the model, we will control for factors such as decisional control preferences, relevant attitudes, health literacy, number of boosters received, disease severity, co-morbidities, whether there is an available clinical trial for the patient, and if so, characteristics of the trial (e.g., difficulty, complexity). At the physician level, we will control for relevant racial and professional attitudes, and decisional control preferences. Because the physician-focused phase involves a quasi-experimental design, we will also control factors that might threaten the internal validity of the intervention, such as time since study has begun, and number of previous interactions between patients and physicians.

Hypothesis 1a. Outcomes will be significantly improved in the patient intervention group, relative to the usual care group. To test hypothesis 1a, we will fit separate MLMs to examine continuous and binary outcomes assessed during or after each visit in which a trial was discussed. The focal independent variable will be the dummy-coded variable indicating whether the patient was in the usual care or intervention group. Support for hypothesis 1a will be indicated by a significant coefficient for this independent variable (i.e. intervention/usual care).

Hypothesis 1b. Outcomes will be significantly improved for patients after the physician intervention, as compared to outcomes before the physician intervention. The focal independent variable is the dummy-coded variable indicating whether or not the patient's physician has received the physician intervention at the time of the clinic visit. Note that this variable is a within-subject variable among the physicians; however, because we theorize that the patient-physician communication quality is central to offers and acceptance of clinical trials, this variable is introduced in the model at level-1 (patients). Support for hypothesis 1b will be indicated by a significant physician-intervention coefficient (i.e., pre/post physician intervention).

Hypothesis 1c. The combined effects of the two interventions will be multiplicative, rather than simply additive. The focal independent variable is the dummy coded variable for the product interaction term in the model. We expect the physician intervention to be more effective among patients who received the patient intervention; we expect a statistically significant positive coefficient for the interaction term.

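### The primary decision model sets about 12–14 controls and three intervention terms against about 65 expected successes, which modestly exaggerates a real effect and costs precision; the list should be shortened and fixed in advance

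*Combined protocol and SAP*

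**What the plan says.** - **Controls.** The Control variables paragraph (Models for Aim 1) begins: "At the patient level of the model, we will control for factors such as decisional control preferences, relevant attitudes, health literacy". It goes on to boosters, disease severity, co-morbidities, availability of a trial, and trial characteristics, with difficulty and complexity as examples. Next: "At the physician level, we will control for relevant racial and professional attitudes, and decisional control preferences". For the quasi-experimental phase it adds elapsed study time and the number of earlier patient-physician interactions. The patient-level list is illustrative. No final list, coding, selection rule, penalised fit or unadjusted fallback is given.
- **Intervention terms.** Models for Aim 1 puts both interventions and their product into one multilevel model per outcome. Aim 2 adds race interactions.
- **Sample and rates.** Participants and Recruitment states: "our estimated sample for the primary analyses is 216 patients who will be video recorded discussing a trial with a participating physician". Power and Sample Size Estimates assumes: "With 24 physicians and 9 patients per physician (i.e., 216 patients), a Type I error rate (α) of .05, and ICC of .05". It sets the "probability of success under the null hypotheses" at .25 and the alternative at .35. Covariates are not mentioned there.
- **Type of model.** The power section defines the primary outcome as binary (the patient decides to enroll or not). The modelling paragraph that follows names multinomial logistic regression for a yes/no/undecided decision.

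**The concern.** Maximum-likelihood logistic estimates drift away from the null when there are few events per estimated slope, and their model-based standard errors tend to run below the true sampling SD. Here the affected quantity is the odds ratio on the primary outcome. If the trial finds a real effect, the reported size would be somewhat too large, and each unneeded control would cost precision that the trial can ill spare.

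Two groups of controls look poorly chosen for the main model:
- The physician scales are constant within a physician, while patients are randomised within physician blocks, so these scales do little to protect the booklet contrast.
- The booster count appears to refer to the reminder cards. These are part of the physician intervention and exist only after it, so adjusting for them adjusts for the intervention itself.

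An open list also leaves the final choice of covariates until after the data are seen.

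**Working it through.** **1. The plan's own figures.** Odds ratio = (.35/.65)/(.25/.75) = 1.615, and its log is .480, so the stated b = 0.48 and 1.61 reproduce (1.62 when rounded up). The stated "odds-ratio = 1.61) with power > .99" does not. With 108 per arm, SE = √[1/(108 × .1875) + 1/(108 × .2275)] = .300, so z = .480/.300 = 1.60 and two-sided power is about .36. That is a separate matter and arises before any covariate enters. It matters here only because it shows that precision is scarce.

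**2. Controls.**
- Patient level: decisional control preferences, attitudes, health literacy, boosters, severity, co-morbidities, trial availability, difficulty, complexity = 9 (8 if trial characteristics count once).
- Physician level: racial attitudes, professional attitudes, decisional control preferences = 3 (2 if attitudes count once).
- Timing: study time, previous interactions = 2.
- Total: 14 (finer count) or 12 (coarser).

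With three intervention terms this gives 17 or 15 slopes. Entering each attitude scale separately would raise the count. Trial availability is probably constant among patients who discuss a trial; dropping it from the finer count gives 16.

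**3. Events per slope.** Expected successes = 108 × .25 + 108 × .35 = 64.8 (1:1 assumed). The range is 54.0 if the rate is .25 throughout and 75.6 if .35 throughout.

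| Slopes | 54.0 | 64.8 | 75.6 |
|---|---|---|---|
| 15 | 3.6 | 4.3 | 5.0 |
| 17 | 3.2 | 3.8 | 4.4 |

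Aim 2 adds race, two 2-way terms and one 3-way term: 64.8/21 = 3.1.

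**4. Consequence by simulation** (216 patients, 24 physicians, ICC about .05, independent normal controls, no missing data).

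*Random-intercept logistic model, dummy coding, true log OR .480:*

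| Terms | Mean log OR (OR) | Mean model SE | Empirical SD | Coverage |
|---|---|---|---|---|
| 3 intervention terms | .500 (1.65) | .444 | .452 | – |
| 3 + 14 controls | .532 (1.70) | .473 | .498 | 94.8% |

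With 17 terms, inflation is .532/.480 − 1 = 11% and the SE ratio is .473/.498 = .95. Across scenarios the inflation is 11–14% (OR 1.70–1.73), the SE is 2–5% low, coverage is 94.4–94.8% and type I error is 4.9–5.4%. With a true OR of 1 the mean log OR is .007.

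*Ordinary logistic fit, interventions coded ±.5:* with 14 controls the mean is .52 (OR e^.52 = 1.68; .52/.48 − 1 = 8%), SE .340 against SD .360 (ratio .944, so 6% low), coverage 94.6% and type I error 4.6%. With three prognostic covariates only, the mean is .49 and the SD .327. Variance ratio: (.360/.327)² = 1.21. A repeat run gave SDs of .353 and .314, a ratio of 1.26, so about 20% is the cautious end. Standard errors are smaller here than in the table because ±.5 coding averages the booklet effect over both phases.

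**5. Fewer decisions.** The 216 are patients expected to be eligible for a trial, and follow-up can end after four visits without an offer. At an assumed 144 decisions, successes are 72 × .25 + 72 × .35 = 43.2, or 43.2/17 = 2.5 per slope. Type I error is then .071 and coverage 93%.

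**6. Phase-linked controls.** With study time and boosters both tied to phase (assumed), the SE of the pre/post term rises from .44 to .92 and its power falls from .18 to .10. The two contributions were not separated.

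**7. Multinomial version.** Slopes double to 34. With 10–20% undecided (assumed), the yes-versus-no log OR is 7% too large (.540/.504 and .576/.537), the SE is 5% low and coverage is about 94.5%.

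**The case against.** The strongest reply is that the harm is small. At 216 patients coverage and type I error hold up and a null effect is not biased. Up to about 4–6 points of the 11–14% inflation in the random-intercept runs already appear with the three intervention terms alone. All of that stands.

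A reader might go further than the documents allow in three ways:
- **Intervals too narrow, or false positives inflated.** This is not borne out at 216. The reported SE rises when controls are added (.444 to .473); it merely rises by too little.
- **Fourteen controls as a minimum.** The coarser count gives 12. Reaching 18 means counting scales named among the questionnaires but not in the control paragraph. A type I error of .065 belongs to that 18-control case only.
- **A fixed, overfitted model.** The text describes models generally and leaves the list open, so part of the defect is missing specification.

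Two further points stand in part. The variance comparison favours the short list, because its three covariates were prognostic by construction. Also, a random-intercept model uses between-physician information, so physician attributes could confound the pre/post contrast if pre/post proportions differ between physicians. That is a reason to keep the long list as a sensitivity analysis, and to retain the controls the plan added to protect that contrast.

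**Conclusion.** The concern holds in a moderate form. About 12–14 listed controls and three intervention terms face about 65 expected successes, roughly 4 per slope. A true log odds ratio of .48 is then exaggerated by about 8–14%, the model SE is about 2–6% too small relative to the true sampling SD, and sampling variance is about 20% larger than with three prognostic covariates. This exaggerates a real effect and loses precision; it does not create one where none exists. Error rates become a concern only if clearly fewer than 216 patients reach a decision.

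The sizes rest on 1:1 allocation, the plan's own rates, independent normal controls with modest or no effects, and complete data. The multinomial reading changes the figures little.

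**What to change.** For the primary decision outcome:

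1. Pre-specify a short baseline list, for example race, site, Time 0 receptivity to discussing a trial, and disease severity at entry.
2. Keep study time, previous patient-physician interactions and trial characteristics, because the pre/post contrast (Hypothesis 1b) is not randomised.
3. Leave out the number of boosters.
4. Move the physician attitude scales from the Aim 1 main model to the exploratory moderator analyses.
5. Report a Firth-type penalised fit as a check. In simulation with 18 controls it gave .478, against .542 from ordinary maximum likelihood and a truth of .48.
6. Report the long list as a sensitivity analysis.
7. Reconcile the binary definition of success with the multinomial model, stating which is primary and how undecided patients are handled.

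The revised model has 3 + 4 + 2 + 1 or 2 = 10 or 11 slopes, so 64.8/10 = 6.5 or 64.8/11 = 5.9 successes each. That improves on about 4 but falls short of the three-covariate comparator (64.8/6 = 10.8), so only part of the simulated gain should be expected and the penalised check is still needed.

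The cost is SAP wording and slightly less adjustment in the main model, which the sensitivity analysis covers.

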Our proposed intervention is driven by an **innovative conceptual model** (Figure 1) derived from our 15 years of novel, transdisciplinary clinical research on patient and physician communication, cancer clinical trials, and racial/ethnic health disparities. Our intervention translates well-validated theories from social psychology and communication science that have never been applied to address the critical need for increasing trial enrollment. Also, whereas prior interventions to improve rates of trial enrollment have generally focused on a single level, the proposed intervention addresses this complex problem by influencing multiple levels—*patients'* trial-related attitudes and communication, *physicians'* trial-related attitudes and communication, *patient-physician clinical interactions* during which trials may be discussed, and ultimately, rates of trial participation by African American (and White) patients. The research is also **methodologically innovative**. Our research design combines a randomized trial with an interrupted time series quasi-experiment.³⁰ Also, we will collect multiple data sources that will allow us to examine processes through which the intervention influences outcomes: patient and

physician self-reports, patient medical records, and video recordings of clinical interactions using our state-of-the-art video recording³¹ and observational coding systems.³²⁻³⁴ In the next paragraph, we explain the conceptual model that informs our proposed research.

Conceptual Model (Fig. 1). Our model proposes that patient and physician individual attitudes and beliefs prior to a clinic visit and their interpersonal communication during the clinic visit interact to directly and indirectly influence outcomes related to patients' decisions about trial participation. We focus on patients who are eligible for clinical trials because, despite their eligibility, only a small percentage enroll in a trial.^{21,35} We focus on physicians because, although other providers such as research nurses are critical to enrolling patients in trials, physicians make the final decision about whether to offer a trial to specific patients³⁶ and patients generally learn about trials, at least initially, from their physicians. Also, patients consider physicians to be their primary and

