Time 0: Patient Recruitment: Participating physicians (or their designee with a clinical relationship) will examine their daily clinic schedule to identify eligible patients who will visit the clinic for a scheduled appointment. We received a waiver of HIPAA documentation to confirm participant inclusion eligibility, and written HIPAA documentation will be obtained at consent. Physicians (or designee) will inform these patients about the study and provide them with a study flyer during or immediately after the visit. (See Appendix E: Flyer). If patients are interested, clinic/research staff will meet with them as soon as possible to explain the study and obtain consent (See Appendix A: Patient Consent Form). At this point, patients will be assigned an ID number and will be asked to complete questionnaires on a tablet device (i.e., iPad) via Qualtrics. Qualtrics is widely used for data collection in both medical and nonmedical settings, and follows very high-level security procedures to protect participant data. The Qualtrics system encrypts data before transmission and is HIPAA compliant. Patients will be asked to complete questionnaires (See Appendix F: Patient Time 0 Questionnaires) including: demographic information, date of prostate cancer diagnosis, preferences for future contact (during study participation), health status, perceived economic burden, health literacy, trust in the medical profession, group-based medical mistrust, and receptivity to discussing a clinical trial. We anticipate these questionnaires will take approximately 20 minutes. Patients will receive a \$20 gift card at this time. Then, clinic/research staff will track patients' scheduled visits until they become potentially eligible for an available clinical trial.

Time 1: 1-2 Weeks Prior to First Clinic Visit After Enrollment: Prior to a patient's scheduled appointment with a participating physician, clinic/research staff will determine whether the patient is potentially eligible for an available clinical trial. If there is no trial available, the patient will not be contacted, and tracking will continue until

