the next scheduled visit. If/when the patient is found to be potentially eligible for an available trial, clinic/research staff will contact him according to the communication/contact preferences he provided at Time 0. They will remind him about the study and ask him if he is willing to meet with research staff at a convenient place and time to complete the Time 1 (baseline) questionnaire (Appendix G: Time 1 Questionnaires), again administered to the participant through Qualtrics on a tablet device (e.g., iPad) or over the phone. The research staff will NOT directly inform patients about their eligibility. If asked, they will tell patients this is up to the physician and clinical staff. Once the questionnaire is completed, an automated computer program provided by Qualtrics will randomly assign the patient to either the usual care or intervention group. Intervention group patients will receive the intervention at this time, or prior to their upcoming appointment, in the form of a booklet (See Appendix M: Patient Intervention Booklet; see below for details). All patients will receive a \$20.00 gift card and be told that their next clinic visit may be video recorded. This visit should take < one hour.

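### The model testing H1b and H1c adjusts for patient attitudes that, in the post-training half, are measured after contact with a trained physician, so it can hide part of a physician effect

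*Combined protocol and SAP*

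**What the plan says.** **Recruitment of the second half.** Under Participants and Recruitment, half of the patients are recruited before the physician intervention and the rest "immediately following the physician intervention; these patients will participate actively until they receive a trial offer or until data collection ends".

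**Time 0.** Candidates are found on the participating physician's clinic schedule. "Physicians (or designee) will inform these patients about the study and provide them with a study flyer during or immediately after the visit". For those interested, "clinic/research staff will meet with them as soon as possible to explain the study and obtain consent", and the questionnaires follow. They include "trust in the medical profession, group-based medical mistrust, and receptivity to discussing a clinical trial".

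**Time 1.** Once a patient is potentially eligible for a trial, he is asked to "complete the Time 1 (baseline) questionnaire". Randomisation to booklet or usual care comes after it. A patient with no available trial is simply tracked to his next visit, so further visits may precede Time 1.

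**Analysis.** Models for Aim 1 uses one multilevel model per outcome for H1a, H1b and H1c. Under Control variables, at the patient level, "we will control for factors such as decisional control preferences, relevant attitudes, health literacy" and further items are adjusted for. H1b is judged on the pre/post physician-intervention coefficient from that model. The plan does not say which attitude scales are meant or from which time point, and it plans no H1b analysis without them.

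**Conceptual Model.** The plan holds that "patient and physician individual attitudes and beliefs prior to a clinic visit", together with communication in the visit, influence the decision about trial participation.

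**The concern.** Whether a covariate is a baseline depends on the intervention being tested. For the booklet, Time 0 and Time 1 both precede allocation, so adjustment is sound. For the physician training, the order is reversed in the second half: the man has already attended a visit with a trained physician when he first reports his attitudes. In the first half, the same scales follow a visit with an untrained physician. A difference in these scores between the halves may therefore be partly a result of training.

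The training covers general communication skills as well as trial discussions (Physician Intervention), so an ordinary visit could carry some of its effect. If it raises receptivity to trial discussion, for example, and receptivity raises the chance of deciding to enrol, holding receptivity fixed takes that route out of the H1b coefficient. A null H1b could then mean that training did not work, or that the model had adjusted away part of its effect. The planned analysis cannot tell these apart.

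**Working it through.** **1. Order of events in each half**

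| Step | First half | Second half |
|---|---|---|
| Visit at which the study is introduced | untrained physician | trained physician |
| Consent, then Time 0 scales | after that visit | after that visit |
| Time 1 questionnaire | later | later |
| Booklet randomisation | after Time 1 | after Time 1 |

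No patient questionnaire comes before the recruitment visit. Decisional control preferences are not in the Time 0 list and their time point is not given, but the same ordering applies to them. The physician-level attitudes are not affected: physicians complete their baseline within a week of their own recruitment, before training.

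**2. The plan's own effect size (Power and Sample Size Estimates)**

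b = ln(.35/.65) − ln(.25/.75) = −0.619 + 1.099 = 0.480, and exp(0.480) = 1.615. This agrees with the plan's 0.48 and 1.61. The stated power above .99 does not reproduce for a two-group comparison: with 216/2 = 108 per half, two-sided power is .36, or .38 with a within-physician design effect of 1 − .05 = .95. That is a separate matter, and this point does not rest on it.

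**3. What adjustment would remove if attitudes shift**

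Let A be a standardised attitude score with mean 0 in the first half and mean δ in the second (SD 1), and let logit P(decides to enrol) = a + t·Post + g·A. Choose a and t so that the overall rates are .25 and .35. The adjusted model then estimates t rather than the total effect. Because the second-half rate depends on t + gδ, t(δ) = t(0) − gδ. For g = 0.5, t(0) = 0.504, so at δ = 0.2, t = 0.504 − 0.100 = 0.404 and OR = exp(0.404) = 1.50.

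δ and g are assumptions; the documents give neither. The remaining risk difference is standardised to first-half attitudes.

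| g (log-odds per SD) | δ (SD) | Adjusted OR | Remaining risk difference | Share of .10 removed |
|---|---|---|---|---|
| 0.3 | 0 | 1.63 | .100 | 0% |
| 0.3 | 0.1 | 1.58 | .093 | 7% |
| 0.3 | 0.2 | 1.53 | .087 | 13% |
| 0.3 | 0.3 | 1.49 | .080 | 20% |
| 0.5 | 0 | 1.65 | .100 | 0% |
| 0.5 | 0.1 | 1.57 | .089 | 11% |
| 0.5 | 0.2 | 1.50 | .079 | 21% |
| 0.5 | 0.3 | 1.42 | .068 | 32% |
| 0.8 | 0 | 1.71 | .100 | 0% |
| 0.8 | 0.1 | 1.58 | .084 | 16% |
| 0.8 | 0.2 | 1.46 | .068 | 32% |
| 0.8 | 0.3 | 1.35 | .053 | 47% |

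At δ = 0 the adjusted odds ratio lies slightly above 1.615 because odds ratios are not collapsible. The risk-difference column is therefore the fairer measure of loss.

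**4. Simulated power for H1b** (1,500 runs, 108 per half, two-sided .05, physician clustering ignored)

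| g | δ | Without A | With A |
|---|---|---|---|
| 0.5 | 0 | .37 | .38 |
| 0.5 | 0.2 | .35 | .25 |
| 0.5 | 0.3 | .36 | .21 |
| 0.8 | 0.3 | .35 | .13 |

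The illustration pools the booklet arms and assumes that the halves differ only through training. H1c was not calculated. Allocation follows both questionnaires, so any shift would be common to both arms, and I would expect less effect on the interaction than on H1b.

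**The case against.** The strongest reply is that the bias is possible rather than shown.

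- **Scales not named.** The covariate rule gives examples only, and the content of Time 1 is in an appendix not available here. Reading relevant attitudes as the Time 0 or Time 1 scales is natural but not stated.
- **Scales largely general.** Two of the three attitude scales at Time 0 concern the profession and group-based mistrust, and may be fairly stable. Trust in the physician is modelled as an outcome and is not named as a covariate. Receptivity is the scale closest to the training.
- **Intended route.** The Overview assigns patients' attitudes to the booklet, and physicians' attitudes and communication to the training.
- **Diluted exposure.** A designee may introduce the study, the visit may not concern a trial, patients may have seen the physician for up to a year, possibly before training, and the reminder card comes only once a patient is potentially eligible.
- **Direction.** H1b compares different, non-randomised patients. Training could change who enrols. If more mistrustful men join afterwards, leaving attitudes out biases H1b downward and adjustment helps.

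The first four bear on whether there is a shift and how large it is; none changes the order of measurement. The last stands in full: an attitude measured after exposure mixes confounding with mediation, so neither model alone settles H1b. That is a reason to report both.

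A reader might infer that the planned model does remove part of the physician effect. The documents do not support this, because they neither name the scales nor show that a visit with a trained physician moves them.

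**Conclusion.** The point holds as a conditional one. The order of measurement and the shared model are in the text. In the second half, the Time 0 and Time 1 attitudes are baselines for the booklet but not for the training, and H1b is judged only after patient attitudes and decisional control preferences have been adjusted for. If training shifts those measures and they affect the decision, H1b can be wrongly unsupported.

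The size cannot be found from the documents. Over the assumed range the loss is 7% to 47% of the .10 difference, with an adjusted odds ratio of 1.58 down to 1.35; with no shift it is zero. A reader might take this range as an estimate of bias, but it is only a sensitivity range. H1a is not affected.

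**What to change.** In Models for Aim 1:

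1. Name the patient attitude and preference scales used as covariates, and their time points.
2. Estimate H1b and H1c in a model without patient attitudes and preferences measured after contact with a trained physician. Keep race, demographics, health literacy, disease severity, co-morbidities, trial availability and characteristics, calendar time, and number of previous interactions.
3. Report the attitude-adjusted model beside it as a labelled sensitivity analysis.
4. Keep Time 0 and Time 1 attitudes as covariates for the randomised H1a comparison. Use no Time 2 attitude score as a covariate.
5. Define the number of boosters, listed in the same sentence. If it means the reminder cards, which the Physician Intervention section describes as a booster, it is part of the physician intervention and should also stay out of the H1b and H1c model.

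The cost is SAP wording and a second model per outcome, because H1a would no longer share its covariate set with H1b and H1c. The downside is that if the halves differ in attitudes for reasons other than training, including who enrols, the main H1b estimate does not adjust for it. The paired analysis shows how much that matters.
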